5.4.2 Secondary Endpoints

Secondary outcomes will be analyzed using similar procedures to the primary outcome. Descriptive statistics for secondary outcome measures will be calculated. Outcomes will be compared between treatment groups using GEE methods (where needed to account for twins) with logistic regression (dichotomous outcomes), linear regression (continuous outcomes), or survival analysis (survival time outcomes), as appropriate. If indicated, these models will be expanded to include baseline covariates and potential interactions between baseline factors and intervention.

Standard data and regression diagnostics will be used to assess model adequacy and examine potential outlying or influential data points for all of the above analyses. If these analyses suggest significant skewness or other violations of parametric model assumptions, the comparisons above may be supplemented with non-parametric methods based on rank scores within the generalized Mantel-Haenszel testing framework, adjusting for clustering of multiple births.

5.4.3 Group Sequential Boundary for Primary Endpoint

To avoid inflating the overall Type I error rate for the primary analysis of efficacy, an O'Brien-Fleming boundary will be used to calculate the nominal significance level to which the interim p-value for the primary endpoint is compared. The efficacy boundary is 0.038 at the final analysis.

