6.1. Statistical Plan

6.1.1. Sample Size Determination

Sample size is based on a possible reduction in risk of neonatal mortality/BDP in infants at 36 weeks PMA receiving the SI intervention compared to those who receive the standard PEEP/CPAP. The significance level was set at $\alpha=0.038$ (due to the interim analyses), and power at 80%. Based on information from the recent multi-center NICHD SUPPORT trial² and the COIN trial,²⁰ we estimate that the baseline rate of neonatal mortality/BDP in the standard or care (control) arm by 36 weeks is 65%.

In order to detect an absolute risk reduction of 12.5%, 263 subjects per treatment arm are required. We anticipate virtually no loss to follow-up for the primary endpoint as infants will likely still be hospitalized because of their condition, will be under constant and continuing medical care. We have inflated the estimate by 1.12 to allow for twins and multiples to be randomized together. With this inflation in mind, the target sample size for this study is 300 subjects per arm.

For the secondary outcomes available in all subjects, with 263 subjects per arm (ignoring the twin correction factor), there will be 80% power to detect a difference of 0.24 standard deviation units in continuous outcomes, and a hazard ratio of 0.77 in survival outcomes under a proportional hazards assumption. Some secondary outcomes will not be available due to death of the infant, or loss to follow-up after discharge from the NICU. Overestimating these rates at 50%, we assume 130 subjects per arm will be available for the longer term secondary outcomes. With this sample size we will still have sufficient power to detect a clinically meaningful difference of at least 17% in event rates (or odds ratio of at least 2.0).

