4. INTERIM ANALYSIS

Since neonatal safety is a consideration in this study, we have chosen to use a group sequential design. Thus, in addition to the final analysis, there will be two interim statistical analyses during the course of this study. The purpose of the interim analyses will be to determine whether or not there is sufficient evidence of a difference between the treatment arms in the primary endpoint such that the trial should be discontinued prior to reaching the target accrual goal.

Interim analyses will be performed after approximately 1/3 (200 subjects) and 2/3 (400 subjects) of the total required patients have completed their primary outcome. An additional safety review will be undertaken after 1/6 (100 subjects) have completed their primary outcome. The results of the interim analyses will be presented to the SAIL Data Safety and Monitoring Committee (DSMC). The primary outcome for the interim analyses will be the comparison of death/BPD between the treatment arms. This comparison will be accomplished by means of a simple generalized estimating equation (GEE) model for death/BPD versus treatment (since adjustment for deliveries with multiple babies will be needed). An approximate O'Brien-Fleming boundary will be used at each interim look to calculate the nominal significance level to which interim p-values are compared (O'Brien PC, 1979). Using the O'Brien Fleming spending function, the three analyses (2 interim + final) should use the following incremental α values (0.0002, 0.012, and 0.038) in order to achieve an overall α =0.05.

There are four comparisons to warrant early stopping: (1) Clear superiority: Superiority of the intervention is sufficiently large that the study should be discontinued because equipoise is lost and randomization should no longer proceed. (2) Futility: The evidence in favor of the intervention is such that at the completion of the study, there is inadequate power to detect an improvement and the study should be dropped. (3) Inferiority: The evidence shows that the intervention is worse than the control and the study needs to be stopped. (4) Safety: Secondary safety outcomes that are considered serious adverse events possible related to the study are clinically higher in the intervention group. (See also section 4.4 for additional safety outcomes).

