4.1 Blinding

The study will be blinded in treatment allocation; patients, parents and clinicians will be unblinded once treatment is assigned; and then blinded analyses. All analyses provided to the DSMC will be provided by intervention, but with the individual interventions identified only as A and B. The same code will be used for each intervention throughout the report. A sealed envelope with the codes for these interventions will be provided to the chair of the DSMC, to allow the DSMC to unblind these results if needed for safety reasons. These codes are also maintained by a member of the DCC who is not involved in the group trials and are not made

available to any other DCC members, including the statisticians. None of the personnel in the DCC, including the statisticians, will have access to these codes until the study has been completed, all data are entered and verified in the database, and the DSMC has approved unblinding of the intervention results.

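### The final-analysis boundary of 0.038 is the alpha spent at the last look, not a p-value threshold; the overall error is about 4.2%, not the stated 5% (a conservative error)

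*SAP*

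**What the plan says.** SAP 4 says that an approximate O'Brien-Fleming boundary serves "to calculate the nominal significance level to which interim p-values are compared". It then says that the three analyses "should use the following incremental α values (0.0002, 0.012, and 0.038"), "in order to achieve an overall α =0.05". Protocol 6.2 gives the same three values and makes the same claim. The looks come after about 200 and 400 of 600 infants, and SAP 5 makes all tests two-sided.

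SAP 5.4.3 returns to the primary endpoint: "an O'Brien-Fleming boundary will be used to calculate the nominal significance level to which the interim p-value for the primary endpoint is compared". Its next sentence is the rule itself: "The efficacy boundary is 0.038 at the final analysis".

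Protocol 6.1.1 sizes the trial at the same level: "The significance level was set at $\alpha=0.038$ (due to the interim analyses), and power at 80" percent. Protocol 6.1.2.2 and SAP 5.4.1 also quote 80% power at 0.038. No section describes 0.038 as deliberately stricter than the design requires.

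**The concern.** A spending function gives the amount of type I error used at each look. The p-value threshold at a look (the nominal level) is a different quantity. It is found from the joint distribution of the test statistics, so that the chance of crossing now, not having crossed before, equals the amount spent. Because the statistics are correlated across looks, part of the final rejection region belongs to trials that have already stopped. The final nominal level is therefore larger than the final increment.

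SAP 4 labels the three values as increments, and SAP 5.4.3 uses the last one as a nominal level. If so, the stated overall alpha of 0.05 and the stated final boundary cannot both be right. At stake is the only explicit final decision rule for the primary endpoint. A final p between 0.038 and the true 5% level would fail SAP 5.4.3, yet would pass the 5% design described in SAP 4 and Protocol 6.2.

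**Working it through.** **Inputs.** Looks at t = 1/3, 2/3 and 1; overall two-sided alpha 0.05; O'Brien-Fleming-type spending (SAP 4, Protocol 6.2). Event rates 65% vs 52.5% (a 12.5-point reduction), 263 per arm, inflation factor 1.12, 300 per arm (Protocol 6.1.1).

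**1. Reproduce the plan's three values.** The cumulative spending is α(t) = 4·[1 − Φ(z/√t)], with z the upper 0.0125 point of the normal distribution. It gives 0.000207, 0.012097 and 0.05. The increments are the differences between successive values.

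| Look | Plan | Increment | Nominal level | z |
|---|---|---|---|---|
| 1/3 | 0.0002 | 0.00021 | 0.00021 | 3.710 |
| 2/3 | 0.012 | 0.0119 | 0.0120 | 2.511 |
| 1 | 0.038 | 0.0379 | 0.0463 | 1.993 |

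The plan's values are the increments. They sum to 0.0002 + 0.012 + 0.038 = 0.0502, which is 0.05 within rounding. At the first two looks the increment and the nominal level agree at the precision printed, so the confusion does no harm there. At the last look they differ.

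**2. Overall error of the written rule.** The three thresholds were treated as nominal p-values, and the joint distribution was integrated recursively with independent increments. The error spent is 0.0002 + 0.0119 + 0.0302 = 0.0423. A simulation of 8 million trials gave 0.0422. With the first two thresholds unchanged, the final level that brings the total to 0.0500 is 0.0463. The gap is 0.0500 − 0.0423 = 0.0077.

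**3. Could another O'Brien-Fleming version give 0.038?** The classical boundary with three equal looks (constant 2.004) ends at 0.0451. The alternative spending form 2·[1 − Φ(z₀.₀₂₅/√t)] ends at 0.0439. Neither gives 0.038.

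**4. Sensitivity to timing.** With looks at 25–40% and 60–75% of information, the spending function's final nominal level is 0.044 to 0.048. The overall error of the fixed 0.0002/0.012/0.038 rule is 0.041 to 0.043.

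**5. Sample size.** The two-proportion formula with pooled variance under the null, at 65% vs 52.5% and 80% power, needs 262.6 per arm at 0.038. This matches the plan's 263, for which power is 80.1%. At 0.0463 it needs 248.

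**6. Power with the planned 300 per arm.** The effective size is 300/1.12 = 267.9 per arm. Group-sequential power, from pooled to unpooled variance, is 81.1–81.8% with 0.038 at the end and 83.2–83.8% with 0.0463. The smallest final difference that reaches significance is 8.8 percentage points at 0.038 and 8.5 at 0.0463.

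**7. A result in the gap.** Take 195/300 (65.0%) vs 169/300 (56.3%), a difference of 0.0867. The pooled rate is 364/600 = 0.6067. The variance is 0.6067 × 0.3933 × (2/300) × 1.12 = 0.00178, so SE = 0.0422, z = 2.05 and p = 0.040. This fails 0.038 and passes 0.0463.

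**The case against.** The strongest reply is that nothing is unsafe. A test of size 0.042 is a valid level-0.05 test, and SAP 5.4.3 aims only to avoid inflating the error, which 0.038 does. The trial was sized at 0.038, so the promised 80% power is delivered, and the 2 points lost were never claimed. Read strictly as increments, the sentence in SAP 4 is true. The documents give 0.038 wherever they state a final or design level and never print another threshold, so under the written plan p = 0.040 is simply not significant.

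Most of this stands. The error is conservative, the sizing is right and the effect is small. It does not remove the inconsistency, however. The increments reading makes SAP 4 true only if the final p-value threshold is not 0.038, and SAP 5.4.3 says that it is. Both sections describe the O'Brien-Fleming boundary as giving a nominal level, and about 0.8 percentage points of the stated error go unspent without explanation. Repeating 0.038 in the sample-size section shows that the increment was carried into the sizing; it does not make 0.038 the 5% boundary.

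A further fair point is that relaxing a primary threshold late in a trial is delicate. The fix below is conditional for that reason.

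**Conclusion.** The concern holds. SAP 5.4.3 uses the last alpha increment as the final p-value boundary. The overall two-sided type I error of the written rule is 0.0423, against the 0.05 stated in SAP 4 and Protocol 6.2; the matching final level is 0.0463. The direction is conservative. The cost is about 2 points of power, and a zone of final p-values from 0.038 to about 0.046 in which the stated rule and the stated 5% design disagree. Under the null, that zone has probability 0.0077.

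The figures assume information proportional to the number of infants completing the primary outcome, looks at 1/3 and 2/3, and no adjustment for futility, for which the documents give no boundary. Moving the looks within the range tried does not change the conclusion. The point should be fixed, but it does not threaten the trial's validity.

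**What to change.** Adopt one of two wordings in SAP 4, SAP 5.4.3 and Protocol 6.2.

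**Option A, only if those deciding have seen no comparative interim results.** State: *The final analysis is tested at the nominal two-sided level given by the O'Brien-Fleming-type spending function (overall alpha 0.05) at the information fractions actually observed; with looks at exactly 1/3 and 2/3 this is 0.0463. The value 0.038 is the alpha spent at the final look.* Restate power in Protocol 6.1.1 as about 83–84% with N unchanged, and revise the references to power at 0.038 in Protocol 6.1.2.2 and SAP 5.4.1 to match.

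Results shown "with the individual interventions identified only as A and B" (SAP 4.1) count as comparative, because a two-sided p-value is the same whichever arm is called A. Under Protocol 7.3 the project statisticians run the interim analyses, so any who have done so cannot be among those deciding.

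**Option B, if that condition cannot be met.** Keep 0.038, state that it is stricter than the spending function requires and that the overall two-sided type I error is about 0.042, and remove the claim that the three values achieve an overall 0.05.

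The documents do not show whether the 200- or 400-infant look has been reported, so the record should say which condition applied.

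Neither option needs new patients or data. Option A loosens a primary success threshold, so it needs a dated amendment and a statement of what the deciders had seen. Option B costs only the wording change and leaves the 2-point power loss in place.

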6. INTENT-TO-TREAT ANALYSIS AND MISSING DATA

6.1 Treatment and Study Withdrawals

It is anticipated that there will be a small number of infants who, because of acute clinical deterioration are treated according to the preference of their medical team rather than by study protocol. However, their outcomes will be measured and analyzed according to original allocation by intention-to-treat principles.

It should be noted that infants who discontinue in the trial, particularly in the case of an adverse event, will not be considered withdrawals from the study unless their parent withdraws consent for further follow-up. The parents of such infants will be encouraged to continue in the study in order to provide complete follow-up information. The characteristics at time of randomization for those participants without complete follow-up will be examined; however, there will be limited statistical power to detect any but major differences between these infants and those with complete follow-up. As mentioned above, in order to assess the potential biases introduced by differential withdrawal among intervention arms, a comparison of withdrawal rates will be carried out using the exact conditional test (ECT) version of Mantel-Haenszel methods to adjust for within-center clustering.

Potential effects of withdrawals and other sources of missing data on the statistical analysis and interpretation of results are discussed further below.

6.2 Other Missing Data Considerations

In addition to data that is naturally missing from participants who withdraw from study, it is expected that there may be occasional missing values for other subjects. All attempts will be made to keep missing data to a minimum. Extensive procedures to minimize missing data during the data collection and entry process will be put in place, following standard operating procedures at the DCC. These procedures will be described further in the Manual of Procedures. In addition, since the infants are still hospitalized at 36 weeks PMA as part of routine clinical care, it has been our experience that this type of missing data is minimal. The number of subjects included with each individual analysis will be given with the results. In general, missing data will not be directly imputed in any way.

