4.4. Study Population

4.4.1. Inclusion Criteria

Infants who are born in participating NICUs (which do not use prophylactic surfactant) and who fulfill the following inclusion criteria are eligible for enrollment: (a) Gestational age (GA) at least 23 weeks but less than 27 completed weeks by best obstetrical estimate; (b) requiring resuscitation/respiratory intervention at birth – “apneic, labored breathing, gasping” (as defined in NRP 2011 AAP 6th Edition p. 45.)⁴

The window for determining eligibility is up to 30 seconds. The decision making process in determining if an infant is eligible is to be done simultaneously while performing the initial steps, such as:

- 1) Placing the infant on the resuscitation trolley;
- 2) Suction airway, open airway and proceed with CPAP;
- 3) Wrap the infant in saran wrap/neo wrap for temperature stability;
- 4) Assessment of heart rate and respiratory effort ; and
- 5) Placement of the pulse oximeter probe.

All 5 initial steps take place at the same time by various members of the DR team. This is consistent with the NRP guidelines which allows up to 30 seconds to accomplish the initial steps and determine the need for PPV. This has been independently verified in several sites (Leiden; Ulm; Edmonton; and Hospital University Pennsylvania in repeated simulations).

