Eligibility and Randomization Data Form	Clinical data: meets inclusion criteria and none of exclusion criteria; eligibility confirmed Research: date and time of randomization, and allocation of treatment arm (control vs intervention)	First 30 seconds of birth
Delivery Room (DR) Data Form	RESEARCH DATA collected: time infant is placed on resuscitation trolley; time of specific maneuver; 1 st sustained inflation and exact pressure measurement x 15 seconds; time of 2 nd sustained inflation and exact pressure measurement x 15 seconds; and use of ventilator vs T-piece	Research intervention takes place within the first 30 seconds up to 1 - 2 minutes of life
	Clinical data: time of birth, time of cord clamping, NRP guidelines used in the resuscitation of the infant such as respiratory status; blood gas values including glucose and hemoglobin/hematocrit values; procedures if any (intubation, chest compression, administration of epinephrine; surfactant delivery; UAC/UVC placement; chest tube placement and additional medications; final respiratory status before leaving DR; and outcome of resuscitation. Additional clinical information: date and time of birth, birth weight, Apgar score at 1 and 5 min, and gender	Certain clinical time points as dictated by the resuscitation process in the DR; data should be completed within first 48 hours

Data Collection Topic	Specific Data Elements	Specific time interval
Respiratory function measurements of inflations and physiologic monitoring (Obtained only at a subset of sites)	Inflation characteristics: pressure, flow, tidal volume, exhaled CO ₂ Physiologic monitoring: heart rate, oxygen saturation, delivered oxygen concentration	First 10 minutes of life
Delivery Room Video recording (obtained only at a subset of sites; transferred and destroyed after analysis)	Video recordings of the infant during the initial resuscitation and stabilization	Up to the first 30 minutes of life
Adverse Events	See Section 9.2 for detailed information.	Specific events during the first 10 days of life; thereafter continuing AE reporting structures are in place until the infant reaches 36 weeks GA
SNAPPE Score	Clinical data: severity score that is compiled by using clinical parameters within the first 12 hours of life, such as lowest pH, PaO ₂ and corresponding FiO ₂ and MAP, urine output and presence of seizures	Completed by first week of life

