6.1.2.2. Analysis of Primary Outcome

The primary endpoint to be used for efficacy evaluation is the rate of Death or BPD at 36 weeks gestation age. The primary hypothesis to be tested is that the treatment therapy results in a decreased event rate. Although a proportion's test is used for sample size calculations, rates will be compared using logistic regression, which will allow for control of covariates, as well as investigation of effect modification. Potential covariates include gender, gestational age, initial heart rate, maternal corticosteroids use, and small for gestational age (SGA). Clinical site will be used as a stratifying factor to control for any confounding by site through residual, site-level treatment imbalance. The logistic regression will be estimated using a generalized estimating equation (GEE) in order to adjust for the inherent correlation expected with multiples. Standard regression diagnostics will be used to assess model adequacy, and to examine for potential outlying or influential data points.

Prior studies offer no basis for assuming a priori interactions between treatment arms and subgroups defined by sex, race/ethnicity, gestational age, site or a combination of these groups, beyond that already controlled for in the randomization. For that reason, preplanned tests for interactions with treatment assignment are not warranted, and not powered for. We propose, however, to table all results by subgroups for descriptive purposes and to explore in secondary analyses possible subgroup differences by treatment group, solely for purposes of generating hypotheses for future studies. In particular, there is interest in exploring subgroups defined by:

- Consenting procedure which may vary by site (antenatal vs. deferred consent). While consenting procedure differences may result in some selection bias, this will be implicitly adjusted for with

the already planned clinical site stratification factor. Additionally, the sample size still results in 80% power at $\alpha=0.038$ for the primary outcome even if the selection bias results in a reduced control arm rate.

- Route of treatment (facemask vs. nasopharyngeal tube). While not expected to modify the intervention effectiveness, exploring this difference will be important for future study design and clinical practice.

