5.4 Analysis of Efficacy Endpoints

5.4.1 Primary Endpoint

In addition to the two-sample comparison (Appendix B, Table 5), adjusted analyses of the primary endpoint (death/BPD rate) may be performed. These adjusted analyses of the primary endpoint will rely on logistic regression and generalized estimating equation (GEE, to control for clustering within multiple births) methods to evaluate whether observed differences, if any, are attributable to imbalances in prognostic factors such as gender, gestational age, initial heart rate, maternal corticosteriods use, and small for gestational age (SGA). Standard regression diagnostics will be used to assess model adequacy and examine potential outlying or influential data points for these analyses. If there are clinical or demographic characteristic imbalances between the two treatment arms, a propensity score analysis (via stratification into 5 subgroups, and via inverse propensity treatment weights) will be used to assess the sensitivity of the results to any treatment allocation biases.

Prior studies offer no basis for assuming a priori interactions between treatment arms and subgroups defined by sex, race/ethnicity, gestational age, site or a combination of these groups, beyond that already controlled for in the randomization. For that reason, preplanned tests for interactions with treatment assignment are not warranted, and not powered for. We propose, however, to table all results by subgroups for descriptive purposes and to explore in secondary analyses possible subgroup differences by treatment group, solely for purposes of generating hypotheses for future studies. In particular, there is interest in exploring subgroups defined by:

- Consenting procedure which may vary by site (antenatal vs. deferred consent). While consenting procedure differences may result in some selection bias, this will be implicity adjusted for with the already planned clinical site stratification factor. Additionally, the sample size still results in 80% power at α=0.038 for the primary outcome even if the selection bias results in a reduced control arm rate.
- Route of treatment (facemask vs. nasopharyngeal tube). While not expected to modify the intervention effectiveness, exploring this difference will be important for future study design and clinical practice.

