6.3 Intent-to-Treat Analysis for the Primary Endpoint

An as randomized (formerly called "intent-to-treat") analysis, in which all available data on all randomized participants are included, will be used for the primary endpoint comparison between interventions.

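### With no imputation in general and no rule for missing covariates, an adjusted analysis of death/BPD would be complete-case and could lose randomised infants whom the unadjusted comparison keeps

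*SAP*

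**What the plan says.** SAP 6.2 expects occasional missing values and sets this rule: "In general, missing data will not be directly imputed in any way". It adds: "The number of subjects included with each individual analysis will be given with the results". Neither document says what happens to an infant who has a primary outcome but lacks a covariate. SAP 6.4 discusses missing data for secondary endpoints only.

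SAP 6.3 defines the primary comparison as an as-randomised analysis "in which all available data on all randomized participants are included, will be used for the primary endpoint comparison between interventions".

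On adjustment, Protocol 6.1.2.2 plans logistic regression fitted by GEE and lists candidates: "Potential covariates include gender, gestational age, initial heart rate, maternal corticosteroids use, and small for gestational age (SGA"). SAP 5.4.1 places adjustment beside the two-sample comparison: "adjusted analyses of the primary endpoint (death/BPD rate) may be performed". Its stated purpose is to see whether a difference is explained by "imbalances in prognostic factors such as gender, gestational age, initial heart rate, maternal corticosteriods use, and small for gestational age (SGA").

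On heart rate, the data table in Protocol section 5 names it in one row only: "Physiologic monitoring: heart rate, oxygen saturation, delivered oxygen concentration". That row is marked as obtained at a subset of sites. Protocol 4.4.1 lists this among the initial steps for every infant: "Assessment of heart rate and respiratory effort". SAP 2.3.2 makes delivery-room heart rate secondary endpoint 1, in three categories (<60, 60-100, >100), with no site restriction and no time point.

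**The concern.** A standard logistic or GEE fit omits every record with a missing value in any model term. Under a general rule against imputation, and with nothing else said about covariates, that is what the adjusted analysis would do. Infants who were randomised and have a known death/BPD outcome would leave the model for want of a baseline item.

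Two things are at stake. The first is interpretation. The adjusted analysis exists to show whether baseline imbalance explains the observed difference. If it is run on fewer infants than the unadjusted analysis, a change in the estimate may come from the adjustment or from the change in population, and the two cannot be separated cleanly. The second is power, because the sample-size calculation leaves almost no room for loss.

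Initial heart rate is the covariate where this most needs tidying. It is a candidate in both documents, the word initial is not defined, and no all-site row of the data table names it. In the SI arm, heart rate after the first inflation is a measure of response (Protocol 4.5.2). The recorded value therefore has to be one taken before allocation is known.

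**Working it through.** **Step 1. What the rules imply together.**

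| Source | Content | Consequence |
|---|---|---|
| SAP 6.2 | No imputation, in general | A missing covariate stays missing |
| SAP 6.2 | N reported per analysis | N may differ between analyses |
| Protocol 6.1.2.2, SAP 5.4.1 | Logistic/GEE with covariates | Records lacking a covariate are omitted from the fit |
| SAP 6.3 | All randomised infants in the primary comparison | The unadjusted comparison keeps them |

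**Step 2. Reproduce the planned sample size.** Inputs: control rate 65%, absolute reduction 12.5 points, alpha 0.038, power 80%, inflation factor 1.12, target 300 per arm (all Protocol 6.1.1); two-sided tests (SAP section 5).

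Formula per arm, pooled variance under the null, no continuity correction:

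n = [z(1−α/2)·√(2p̄(1−p̄)) + z(power)·√(p1(1−p1)+p2(1−p2))]² / (p1−p2)²

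- p1 = 0.65, p2 = 0.525, p̄ = 0.5875
- z(0.981) = 2.0749, z(0.80) = 0.8416
- √(2 × 0.5875 × 0.4125) = 0.6962
- √(0.2275 + 0.2494) = 0.6906
- n = [(2.0749 × 0.6962 + 0.8416 × 0.6906) / 0.125]² = 262.6, so 263

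This matches the Protocol exactly. With inflation, 263 × 1.12 = 294.6, and the Protocol sets the target at 300.

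**Step 3. Power when a share m lacks a covariate.** The documents give no value for m, so 5%, 10% and 20% are assumptions. Effective n per arm = 300(1−m)/1.12, and

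power = Φ{[0.125·√n − 2.0749 × 0.6962] / 0.6906}

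| m (assumed) | Infants analysed | Effective n per arm | Power |
|---|---|---|---|
| 0% | 600 | 267.9 | 0.808 |
| 5% | 570 | 254.5 | 0.787 |
| 10% | 540 | 241.1 | 0.764 |
| 20% | 480 | 214.3 | 0.712 |

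**Step 4. The margin.** 80% power needs 294.6 of the 300 per arm, so the tolerable loss is 1 − 294.6/300, about 1.8%.

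These figures ignore any precision gained from adjustment. They describe a complete-case adjusted model only, not the two-sample comparison.

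**The case against.** The strongest reply is that little depends on this. The SAP's adjusted analysis is optional and its covariate list is illustrative; the Protocol calls the covariates potential. The comparison of all randomised infants needs no covariate, and the interim model contains treatment alone. SAP 6.2 says in general, which leaves room for exceptions, and it expects missing values to be few. Reporting N for each analysis would at least make any loss visible. All of this stands, and it limits the point to the adjusted analysis. It does not supply a rule: if a covariate is missing, the plan as written gives no basis for keeping the infant.

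A reader might go further and infer from the data table that heart rate exists only at the monitoring sites, so that most infants would fall out of the model. The documents do not support that. Heart rate is assessed in the initial steps for every infant (Protocol 4.4.1), and a rate below 100 that is not rising is one route to eligibility (Protocol 4.5). Secondary endpoint 1 carries no site limit, whereas endpoint 4 in the same SAP list is marked as available at some sites only. The restricted row groups heart rate with flow, tidal volume and exhaled CO2 over the first 10 minutes, and is best read as monitor recordings. The all-site delivery-room row is open-ended, so an item not named there may still be collected.

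A reader might also infer that the sicker infants are the ones with missing values. Nothing in the documents shows this. Decisions in unstable infants turn on heart rate, so the opposite pattern is as plausible.

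**Conclusion.** The point holds in a limited form. Read as written, the plan makes any covariate-adjusted analysis of death/BPD complete-case, and its population would then depart from the as-randomised set used for the comparison it is meant to check. The size depends on a missing share that the documents do not state. Over an assumed 5% to 20%, between 30 and 120 of 600 infants would be lost, and power in that model would fall from 0.81 to between 0.79 and 0.71, before any gain from adjustment. The unadjusted comparison and its power are untouched. No direction of bias is claimed. For heart rate, what stands is a gap in definition and documentation, not evidence that the value is unavailable at most sites.

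**What to change.** 1. **SAP 6.2, one sentence.** For pre-randomisation covariates only, replace a missing value by a simple value that does not use the treatment arm (such as the stratum mean), or by a missing category, so that every infant with a primary outcome stays in the adjusted model. Randomisation makes baseline covariates independent of arm, so a fill-in that ignores arm does not bias the treatment comparison. The general rule can stay for outcomes.
2. **Initial heart rate.** Define it as the category (<60, 60-100, >100) assessed before the envelope is opened, and confirm that it is recorded on a form used at all sites. If that cannot be confirmed, drop it as a covariate.

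The cost is one SAP sentence, one definition and, if the field is not already there, one form item for an assessment that is already made. The downside is slightly weaker adjustment for infants with a filled-in covariate.
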